5.5 Other Statistical Considerations

The analysis will be conducted in consideration of the following matters, and if separate considerations are needed depending on the analysis item, the contents will be described in the relevant item of '7.1 Derivation'.

- The standard for converting Day into Month or Year is as follows: 1 month = 30.4375 days, 1 year = 365.25 days
- For all data analyses, the test statistic is a two-sided test, and the statistical significance level is based on 0.05.
- When calculating percentages from categorical demographics and baseline data, the denominator is defined as the sum of the number of subjects in each category. However, for analysis by detailed medical history/medication type, the denominator is defined as the number of subjects with medical history/medication.
- When calculating percentages of the incidence of adverse events and valid/invalid by demographics and baseline data, the denominator is defined as the number of subjects in each category. However, upon analyzing by detailed medical history/medication type, the denominator is defined as the number of subjects with medical history/medication in each category.
- When calculating the percentage of the incidence for each type of adverse event, the denominator for analyzing the safety analysis set is defined as the number of subjects in the safety analysis set. However, in the analysis of subjects excluded from safety evaluation, the denominator is defined as the number of subjects excluding those who were investigated in duplicate, those who did not receive this drug, or those who did not undergo follow-up for safety.

- In categorical data, if the cells with an expected frequency of less than 5 are more than 20% of all cells in the between group test, Fisher's exact test is used for analysis instead of the Chi-square test.
- For the confidence interval, a 95% two-sided confidence interval is calculated by applying the exact confidence interval method.
- If the total number of adverse events is 10 or less, the analysis of the incidence of adverse events by demographics and baseline data can be replaced with the list of adverse events.
- Multiple logistic regression analysis is not performed when there are two or less variables that show significant differences in the analysis of the incidence of adverse events by demographics and baseline data.

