#### 8.2.3.2 Visit 1; Baseline Visit

Upon patient enrolment, the following will be recorded on the patient's eCRF.

- Information on the site (Hospital name, Department, Physician name, Contract date)
- Visit date
- Diagnosis: date of the diagnosis of T2DM, Family history of T2DM
- Inclusion / Exclusion criteria
- Informed consent form: Date of Informed consent
- Demographic data: Age, gender, pregnancy, height, smoking status
- Diabetes mellitus related complication (Retinopathy, Neuropathy, Nephropathy, Vasculopathy, etc.)
- Medical history: Hypertension, Dislipidemia, Coronary artery disease, Stroke, Liver disease, Renal failure, Allergy, Nephropathy, etc. (history of concomitant disease within 6 months)
- Physical examination: body weight, blood pressure in sitting position (SBP, DBP)
- Renal Function: record Serum creatinine, eGFR, urin ACR if blood test result is available (the most recent data prior to baseline)
- Effectiveness endpoints: HbA1c, [REDACTED] (Lab data should be collected within 1 month prior to baseline)
- Concomitant anti-hyperglycemic agent : record any anti-hyperglycemic agents have been taken prior to the baseline visit (within 1 month prior to baseline)
- Concomitant medications: record all medications have been taken at least once since one month prior to the baseline visit.
- Dose of JARDIANCE DUO® given(Daily dose(Dosage/Administration), Start date)

At visit 1, the patient will be requested to contact the treating physician in the event of any adverse events noted after initiating JARDIANCE DUO® treatment.

#### 8.2.3.3 Visit 2; 12 weeks from Visit 1

After 12 weeks from Visit 1, the patients will return for follow-up. The followings will be noted and recorded in the eCRF.

- Visit date
- Physical examination: body weight, blood pressure in sitting position (SBP, DBP)

Proprietary confidential information © 2019 Boehringer Ingelheim International GmbH or one or more of its affiliated companies

- Any change of JARDIANCE DUO® given (Daily dose(Dosage/Administration), Start date, Date of discontinuation or continuation, Action taken, Causality)
- Effectiveness endpoints: HbA1c, [REDACTED]
- Renal Function: record Serum creatinine, eGFR, urine ACR if blood test result is available (The most recent data since last visit, except previously entered data)
- Concomitant anti-hyperglycemic agent including new medications taken since last visit : any change in the concomitant medications (dose and dosing intervals)

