### 8.7.2 Safety analysis

- ① Among the subjects of safety evaluation, the number of subjects with adverse event incurred and the number of adverse events incurred should be calculated, and the incidence rate of adverse events and the 95% confidence interval should be presented.
- ② The number and percentage of adverse events by type and category should be presented.

- ③ Analysis should be made using Chi-square test or Fisher's Exact test on the adverse event onset status by demographic data of subjects of safety evaluation.
- ④ To estimate any factors that are thought to influence the analyzed incidence rate of adverse events, logistic regression analysis should be conducted, and for statistically significant parameters, the meaning should be described.

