2.2 Number of Subjects

The sample size of 600 patients is based on the requirement of the local regulatory authority (MFDS). As per regulation, long-term surveillance is necessary for the T2DM indication. Since T2DM is chronic disease it might be restrictive to collect safety and effectiveness data in short-term (12weeks) period, all patients will be enrolled for long-term (24weeks) surveillance.

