6.8.1 Summary of Adverse Events

The number of subjects with adverse events and their incidence (%) for each SOC and PT, 95% confidence interval for the incidence, and the number of cases will be included.

- Adverse events, Adverse drug reactions^a
- Serious adverse events, Serious adverse drug reactions
- Unexpected adverse events^b, Unexpected adverse drug reactions
- Unexpected serious adverse events, Unexpected serious adverse drug reactions
- Non serious adverse drug reaction^c
- Adverse event of special interest(AESI)^d
- Adverse events leading to discontinuation^e

^aAdverse Drug Reaction (ADR): any adverse drug reaction with causality (Certain/ Probable/Likely/ Possible/ Conditional- Unclassified/ Unassessable)

^bUnexpected adverse event: the event is not included in the latest approved local label

^cNon serious adverse drug reaction: any adverse reaction which does not meet the SAE criteria

^dAdverse event of special interest(AESI) is as following 8 events:

AESI (Adverse Event of Special interest)

- Vaginal moniliasis, vulvovaginitis, balanitis and other genital infection
- Increased urination
- Urinary tract infection (UTI)
- Volume depletion
- Diabetic Ketoacidosis (DKA)
- Decreased renal function:
 - Creatinine value shows a >2-fold increase from baseline and is above the ULN
- Hepatic injury defined by the following alterations of liver parameters:
 - An elevation of AST and/or ALT >3-fold ULN combined with an elevation of total bilirubin >2-fold ULN measured in the same blood draw sample.
 - An isolated elevation of AST and/or ALT >5-fold ULN (without an elevation of total bilirubin >2-fold ULN)
- Lower limb amputation
 - Amputation (i.e. resection of a limb through a bone)
 - Disarticulation (i.e. resection of a limb through a joint)
 - Auto-amputations (i.e. spontaneous separation of non-viable portion of the lower limb)

^eAdverse events leading to discontinuation: Reason of early termination is a 'due to Adverse event' and also action taken with study drug is 'Discontinued'

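### Single-sex terms within the genital-infection AESI are reported over men and women together, which dilutes their incidence by the affected sex's share; report them by sex as well

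*SAP*

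**What the plan says.** SAP 5.5 has two relevant denominator rules. For incidence by type of event, "the denominator for analyzing the safety analysis set is defined as the number of subjects in the safety analysis set". For incidence of adverse events "by demographics and baseline data, the denominator is defined as the number of subjects in each category". Section 5.5 refers any item-specific departures to SAP 7.1, which covers age, disease duration, exposure and dose but no adverse event denominator.

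The first rule is applied row by row. SAP 6.8.1 lists "The number of subjects with adverse events and their incidence (%) for each SOC and PT, 95% confidence interval for the incidence", with AESIs among the items, and SAP 6.8.2 repeats this. On the interval, SAP 5.5 says "a 95% two-sided confidence interval is calculated by applying the exact confidence interval method". The first AESI in SAP 6.8.1 (footnote d), and in Protocol 10.1, is "Vaginal moniliasis, vulvovaginitis, balanitis and other genital infection".

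Gender is recorded at Visit 1 (Protocol 8.2.3.2: "Demographic data: Age, gender, pregnancy, height, smoking status") and is a category in SAP 6.3 and 7.2. Protocol 8.7.2 plans the comparison by subgroup: "Analysis should be made using Chi-square test or Fisher's Exact test on the adverse event onset status by demographic data". Neither document states an expected split between men and women.

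**The concern.** Monitoring safety is the primary objective, and genital infection heads the AESI list. A PT row for a vulvovaginal infection will have every man in the safety set in its denominator, and a balanitis row every woman. None of those people can have the event. A prescriber looking at a vulvovaginal row will naturally take the percentage as a woman's risk, and on that reading both the estimate and its confidence limits are too low. The effect is also present when no event is seen: the upper limit then looks tighter than the number of people at risk can support.

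The second rule in SAP 5.5 does use each gender's own denominator. In the text available it concerns whether adverse events occurred, by demographic category, and is not stated to be broken down by PT or AESI.

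**Working it through.** **Inputs.** N = 600 is the planned size (SAP 2.2). I take it as the safety set size; exclusions would lower it, but the dilution factor depends only on the sex share. The share of women f and the event counts are assumptions, because the documents give neither. There is no figure in the plan to reproduce for this point: 600 is a regulatory requirement.

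**Single-sex PT.** Let x be the affected subjects and n_s the number of that sex in the safety set. Then

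x/N = (x/n_s) × (n_s/N),

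so the reported incidence divided by the sex-specific incidence equals n_s/N, whatever the true risk.

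| Assumed share of women | Factor, vulvovaginal PTs | Factor, balanitis |
|---|---|---|
| 30% | 0.30 | 0.70 |
| 40% | 0.40 | 0.60 |
| 50% | 0.50 | 0.50 |
| 60% | 0.60 | 0.40 |
| 70% | 0.70 | 0.30 |

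**Worked examples (assumed counts, exact Clopper-Pearson intervals).**

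- 45% women: 0.45 × 600 = 270. With 16 affected, 16/600 = 2.67% (95% CI 1.53-4.29) as planned, against 16/270 = 5.93% (3.42-9.45). The planned estimate lies below the lower limit of the sex-specific interval.
- 40% women: 14/600 = 2.33%, against 14/240 = 5.83%.
- 55% women: 20/600 = 3.33%, against 20/330 = 6.06%.
- A lower assumed risk, 50% women: 15/600 = 2.50% (1.41-4.09), against 15/300 = 5.00% (2.83-8.11). Balanitis with 6 affected men: 6/600 = 1.00% (0.37-2.16), against 6/300 = 2.00% (0.74-4.30).
- No events, 50% women: the exact upper limit is 1 − 0.025^(1/600) = 0.61% on 600, against 1 − 0.025^(1/300) = 1.22% on 300.

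**Composite AESI.** With risks p_F and p_M, the composite incidence is f·p_F + (1 − f)·p_M. This is exactly what the whole-set ratio estimates, so there is no dilution at any split. In the 50% example, (15 + 6)/600 = 21/600 = 3.50% (2.18-5.30), with or without a change to the PT rows.

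**The case against.** The strongest reply is that nothing here is miscalculated. The number affected over the whole safety set is a valid crude incidence in treated patients, and its exact interval is correct for that quantity. Using it for every PT is a choice of what to estimate. That stands: the rows mislead only when read as the risk in one sex.

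A reader might infer that the genital-infection AESI itself will be under-reported. The documents do not support that, since it is defined as one composite covering both sexes and its whole-set incidence is right. A reader might also infer that the rows show about half the sex-specific risk. That holds only near a 50/50 split, which neither document gives.

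It can also be said that the SAP already uses gender denominators in its by-demographics analysis. It does, but the text available does not extend this to PTs or AESIs, and SAP 5.5 lets a listing replace that analysis when there are 10 or fewer adverse events in total. SAP 6.8 refers to a section 6.8.3 that is not in the text available. It may describe this analysis, so no claim is made about it.

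Finally, the study is single-arm and descriptive, and subject counts per PT and the gender distribution are both to be reported. A reader could therefore recompute the sex-specific percentage and its exact interval. That stands and limits the seriousness: what is missing is a printed result, not information.

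**Conclusion.** The point holds for single-sex PTs only. In the text available, SAP 5.5 has no exception for them, so the vulvovaginal and balanitis rows and their intervals will describe the whole treated population. As statements about the sex at risk they are too low by that sex's share: a factor of 0.30-0.70 over an assumed share of 30-70%. The factor is exact once the split is known; the percentages in the examples also rest on assumed event counts. The composite AESI is unaffected. Confidence is limited by the absence of SAP 6.8.3 from the text available. Because the missing figures can be recovered from reported counts and no decision rule is seen to depend on these rows, this is a cheap improvement rather than a flaw in the primary safety analysis.

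**What to change.** Add one sentence to SAP 5.5: for PTs that can occur in only one sex, incidence and its exact 95% CI are reported with the number of women (or men) in the safety analysis set as denominator. In SAP 6.8.1 and 6.8.2, show the genital-infection AESI separately for women and men, each with its exact 95% CI, beside the whole-set composite, which stays as planned. Label the denominator in each row. If SAP 6.8.3 already gives adverse events by gender at PT or AESI level, a cross-reference from 5.5 would be enough for the display.

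No new data are needed. The cost is the added sentence, the number of women and of men as extra denominators in the adverse event program, and a few more table rows.

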5.6 Reporting Conventions

- P-value is rounded and presented to 4 decimal places.
- If the calculated p-value is less than 0.0001, it is presented as ‘<0.0001’.
- Descriptive statistics (mean, standard deviation, median, minimum, maximum, percentage) are rounded and presented to 2 decimal places.
- If the calculated percentage is less than 0.01, it is presented as ‘<0.01’.

6. Evaluation of Study Data

The analysis set will be applied as analysis group as followings:

[figure not shown]
Analyses	Safety Analysis Set	Excluded from Safety Analysis Set	Effectiveness Analysis Set
Demographics	✓		✓
Medical History	✓		✓
Prior and Concomitant Medication	✓		✓
Study Medication Treatment Status	✓		✓
Safety Evaluation	✓	✓ [†]	
Effectiveness Evaluation			✓

[†] analysis only for 6.8.4 section

6.1 Disposition of Subjects

The frequency and percentage of subjects who enrolled in this surveillance are calculated as followings:

- Total number of enrolled subjects
- The number of subjects in the safety analysis set
- The number of subjects excluded from safety analysis set and reasons
- The number of subjects in the effectiveness analysis set
- The number of subjects excluded from effectiveness analysis set and reasons

6.3 Demographics

- Continuous Data:

- Birth of year
- Body weight

- Categorical Data:

- Gender
- Birth of year
- Smoking status
- Early termination and reasons

6.4 Medical History

- Continuous Data:

- Duration of disease^a

- Categorical Data:

- Duration of disease
- Family history of Type 2 diabetes mellitus
- Diabetes mellitus related complication
- Other Medical history
- Allergy history
- Renal impairment

^a Duration of disease: Total period from date of the diagnosis to start date of this study drug

^b Other Medical history: history of concomitant disease within 6 months prior to baseline

^c Allergy history: history of allergy within 6 months prior to baseline

Detailed disease names of other medical history will be summarized in SOC using the latest version of MedDRA. At this time, even if one subject has two or more medical histories, if they fall under one category, they will be analyzed as one person within the category. Also, one subject may be presented in duplicate in different medical history categories.

In addition, detailed disease names of diabetes complications are analyzed by type as collected in the CRF. At this time, even if one subject has two or more medical histories, if they fall under one category, they will be analyzed as one person within the category. Also, one subject may be presented in duplicate in different medical history categories.

6.5 Prior and Concomitant Medications

- Categorical Data:
 - Concomitant medications^a
 - Concomitant anti-hyperglycemic agent^b

^aConcomitant medications: within 1 month prior to baseline

^bConcomitant anti-hyperglycemic agent: within 1 month prior to baseline except study drug

The presence or absence of medication history of concomitant medications and other antidiabetic agents is presented as descriptive statistics.

The detailed drug names of concomitant medication history will be summarized using KIMS with a major category name and a subcategory name. At this time, even if one subject took two or more drugs, if they fall under one category, they will be analyzed as one person within the category. Also, one subject may be presented in duplicate in different drug categories.

In addition, the detailed drug names of the medication history of other antidiabetic agents are analyzed by type as collected in the CRF. At this time, even if one subject took two or more drugs, if they fall under one category, they will be analyzed as one person within the category. Also, one subject may be presented in duplicate in different drug categories.

6.7 Study Medication Treatment Status

- Continuous Data:
 - Total period of study drug
 - Total dose of study drug (empagliflozin)
 - Total dose of study drug (metformin)
 - Average of daily dose (empagliflozin)
 - Average of daily dose (metformin)
- Categorical Data:
 - Total period of study drug
 - Average of daily dose (empagliflozin)
 - Average of daily dose (metformin)

6.8 Safety Evaluation

Safety analysis set will be analyzed following the section 6.8.1, 6.8.2, 6.8.3, 6.8.5 and excluded from safety analysis set will be analyzed following the section 6.8.4.

6.8.1 Summary of Adverse Events

The number of subjects with adverse events and their incidence (%) for each SOC and PT, 95% confidence interval for the incidence, and the number of cases will be included.

- Adverse events, Adverse drug reactions^a
- Serious adverse events, Serious adverse drug reactions
- Unexpected adverse events^b, Unexpected adverse drug reactions
- Unexpected serious adverse events, Unexpected serious adverse drug reactions
- Non serious adverse drug reaction^c
- Adverse event of special interest(AESI)^d
- Adverse events leading to discontinuation^e

^aAdverse Drug Reaction (ADR): any adverse drug reaction with causality (Certain/ Probable/Likely/ Possible/ Conditional- Unclassified/ Unassessable)

^bUnexpected adverse event: the event is not included in the latest approved local label

^cNon serious adverse drug reaction: any adverse reaction which does not meet the SAE criteria

^dAdverse event of special interest(AESI) is as following 8 events:

AESI (Adverse Event of Special interest)

- Vaginal moniliasis, vulvovaginitis, balanitis and other genital infection
- Increased urination
- Urinary tract infection (UTI)
- Volume depletion
- Diabetic Ketoacidosis (DKA)
- Decreased renal function:
 - Creatinine value shows a >2-fold increase from baseline and is above the ULN
- Hepatic injury defined by the following alterations of liver parameters:
 - An elevation of AST and/or ALT >3-fold ULN combined with an elevation of total bilirubin >2-fold ULN measured in the same blood draw sample.
 - An isolated elevation of AST and/or ALT >5-fold ULN (without an elevation of total bilirubin >2-fold ULN)
- Lower limb amputation
 - Amputation (i.e. resection of a limb through a bone)
 - Disarticulation (i.e. resection of a limb through a joint)
 - Auto-amputations (i.e. spontaneous separation of non-viable portion of the lower limb)

^eAdverse events leading to discontinuation: Reason of early termination is a 'due to Adverse event' and also action taken with study drug is 'Discontinued'

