### 8.3.3 Assessment criteria

#### 8.3.3.1 Assessment of safety

[figure not shown]
- Adverse events (event name/ symptoms/ sign/ identify hypoglycemia symptoms)
- Onset date, End date
- Intensity (Mild/ Moderate/ Severe)
- Serious (Serious/ Non-Serious)
- Outcome of the event (Recovered/ Not yet recovered/ Sequela/ Fatal/ Unknown)
- Causality (Certain/ Probable/Likely/ Probable/ Possible/ Unlikely/ Conditional/ Unclassified/ Unassessable/ Unclassifiable)
- Factors other than JARDIANCE DUO® (None/ Concomitant medication/ Concomitant disease/ etc.)
- Action taken with study drug due to AE (Discontinued/ Reduced/ Increased/ Continue/ Discontinued and reintroduced/ Unknown/ Not applicable)
- Recurrence in reintroduced (Recurrence/ No-recurrence/ Unknown/ Not applicable)
- Adverse Event of Special interest (Not applicable/Vaginal moniliasis, vulvovaginitis, balanitis and other genital infection/Increased urination/Urinary tract infection/Volume depletion/ Diabetic Ketoacidosis, Decreased renal function, Hepatic injury defined by the alterations of liver parameters/Lower limb amputation)

- Investigator's comments(if needed)

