### Collection of AEs

The study design is of non-interventional nature and the study is conducted within the conditions of the approved marketing authorization. Sufficient data from controlled interventional studies are available to support the evidence on the safety and effectiveness of the studied JARDIANCE DUO®. For this reason the following AE collection and reporting requirements have been defined.

All adverse events occurred from the signing date on ICF to 30 days after last administration date of medication need to be collected, documented and reported to the sponsor using the AE reporting form of eCRF ([CRF13.1](#)).

All SAEs, ASAEs and AESIs must be reported within 24 hours of occurrence and via telephone/fax to the Local PV Manager (LPVM) of [REDACTED] using the NIS AE form ([13.2](#)). All non-serious Adverse Reactions associated with JARDIANCE DUO® (empagliflozin/metformin) and pregnancy monitoring forms must be reported within 7 calendar days of occurrence and via telephone/fax to the LPVM of [REDACTED]. If any new or further information to these events is available, a follow-up NIS AE report has to be sent to BI. All SAEs and non-serious AEs must include a causal relationship assessment from the physician.

All ADRs (serious and non-serious), including those persisting after study completion must be followed up until they are resolved, have been sufficiently characterized, or no further information can be obtained.

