**EVENT INFORMATION**

Record all dates in ddmmmyyyy format (e.g. 01Jan2016). If ongoing, enter 'CONT.' Record all times in 24-hour (hh:mm) format. If time is unknown, record 'UNK.'

	Event No. [ ]	Event No. [ ]	Event No. [ ]	Event No. [ ]				
Adverse Event term (if available, enter the diagnosis)								
Onset date								
Onset time								
End date								
End time								
Was the event serious?	 Yes	 No	 Yes	 No	 Yes	 No	 Yes	 No
If serious, please mark reason for seriousness	 Results in death							
	 Immediately life-threatening							
	 Persistent or significant disability/incapacity							
	 Requires/prolongs hospitalisation							
	 Congenital anomaly/birth defect							
	 Other comparable medical criteria (specify in Description of Event section)							
Was the event a protocol-specified Adverse Event of Special Interest (AESI)?	 Yes	 No	 Yes	 No	 Yes	 No	 Yes	 No
Is there a reasonable causal relationship between the Adverse Event and: (provide description of rationale, other possible causes on page 3)								

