6.8.5 Other Safety Analyses

When reporting for re-examination, the following items will be categorized based on the incidence (%) by PT (Preferred Term), and information on SOC (System Organ Classes) and PT (Preferred Term) will be presented in a table.

[figure not shown]
- Serious adverse events, Serious adverse drug reactions
- Unexpected adverse events, Unexpected adverse drug reactions

[figure not shown]
At the time of reporting for re-examination, descriptive statistics of serum creatinine, glomerular filtration rate, and albumin-creatinine-ratio measured before administration of this drug and at the final visit are presented. In order to analyze whether there is a difference at the final visit compared to before administration of this drug, the paired t-test is used.

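### The decreased-renal-function AESI is a numerical creatinine rule, but no stated step checks the recorded creatinine values against the AE records it is tabulated from

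*SAP*

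**What the plan says.** **Definition.** Protocol 10.1 and SAP 6.8.1 (footnote d) give the same criterion for decreased renal function: "Creatinine value shows a >2-fold increase from baseline and is above the ULN". Both parts are laboratory comparisons.

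**How AESIs are recorded.** Protocol 10.2 requires adverse events to be "documented and reported to the sponsor using the AE reporting form of eCRF". Protocol 8.3.3.1 makes the AESI category an attribute of the AE assessment: "Adverse Event of Special interest (Not applicable/Vaginal moniliasis, vulvovaginitis, balanitis and other genital infection/Increased urination", and so on through the remaining categories. The NIS AE form in Protocol 13.2 has a yes/no AESI box for each event.

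**How AESIs are tabulated.** AESI is one of the items that SAP 6.8.1 tabulates from AE records: "The number of subjects with adverse events and their incidence (%) for each SOC and PT, 95% confidence interval for the incidence, and the number of" (the sentence ends with event counts). SAP 6.8.2 repeats this by preferred term.

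**What creatinine data are held.** At Visits 2 and 3 (Protocol 8.2.3.3 and 8.2.3.4) the site is to "record Serum creatinine, eGFR, urine ACR if blood test result is available", using the latest result since the previous visit. Visit 1 has an equivalent instruction for the latest result before baseline. Protocol section 14 shows that the follow-up renal tests were added in the first amendment in order to follow renal function.

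**What is done with them.** SAP 6.8.5 plans "descriptive statistics of serum creatinine, glomerular filtration rate, and albumin-creatinine-ratio" before drug and at the final visit, with a paired t-test. SAP 5.3 defines descriptive statistics as number, mean, SD, median, minimum and maximum.

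**The concern.** The criterion can be applied to numbers the study already asks sites to record, yet the table depends on the investigator noticing that it has been met, opening an AE record and choosing the right category. If a doubled creatinine is entered on the visit page and no AE follows, the described tabulation has no record to count.

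Safety is the primary objective, and AESI incidence is a listed safety endpoint (Protocol 8.3.2.1). AESIs also fall under 24-hour reporting (Protocol 10.2), so an unrecognised case would be a missed expedited report as well as a missing count. Few cases are likely among 600 patients, so one or two missed entries could change what the table shows.

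**Working it through.** The plan states no expected rate for this AESI, so there is no figure to reproduce. The check has a textual part and an illustrative part.

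**1. Is there a stated link from creatinine values to AESI records?**

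- SAP 7.1 derives age, disease duration, administration period, total dose and average daily dose. Nothing is derived from creatinine.
- SAP 7.2 has yes/no categories for renal impairment and renal failure, but none for a rise from baseline.
- Protocol 8.8 describes automatic range, consistency and completeness checks in general terms. None is said to compare creatinine with AE entries.
- Protocol 10.1 describes a query for always-serious events. It starts from an AE already entered, so it cannot find an event with no AE record.

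No link is stated.

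**2. Would the analysis in SAP 6.8.5 show the cases anyway?**

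- *Mean and paired t-test.* Assume a rise from 1.0 to 2.1 mg/dL, a change of 1.1. With k such patients among n, the mean moves by 1.1 × k / n. For n = 600, k = 1 gives 0.0018 and k = 6 gives 0.011 mg/dL. For n = 300 (tests are recorded only if available), k = 1 gives 1.1/300 = 0.0037. Shifts of this size would not be recognised as individual doublings.
- *Maximum.* An extreme final-visit value would appear, but it is not tied to that patient's baseline. With an assumed ULN of 1.2 mg/dL and a baseline of 0.6, any value above 1.2 meets both parts of the rule. Such a value could lie below a maximum set by another patient whose creatinine was already high and unchanged.
- *Timing.* Only the pre-drug and final-visit values enter. A doubling at Visit 2 that resolved by Visit 3 is not used.

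**3. What could a few missed entries do?** Assumptions: 600 patients in the safety set, a true rate p, and a share s of qualifying patients entered as AEs. Neither p nor s comes from the documents. Expected count = 600 × p × s. Chance of a zero count = (1 − p × s)^600.

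| Assumed p | Expected, s = 1 | P(zero), s = 1 | Expected, s = 0.5 | P(zero), s = 0.5 |
|---|---|---|---|---|
| 0.2% | 1.2 | 30% | 0.6 | 55% |
| 0.5% | 3.0 | 5% | 1.5 | 22% |
| 1.0% | 6.0 | 0.2% | 3.0 | 5% |

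Each case is 1/600 = 0.17 percentage points. By the exact method in SAP 5.5, 3/600 is 0.50% (95% CI 0.10 to 1.45) and 1/600 is 0.17% (0.00 to 0.93). Zero cases gives an upper limit of 0.61%.

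**4. Can the rule be applied to the stored values?** The ratio can, wherever a baseline and a follow-up value exist. The ULN part cannot be settled from the listed visit items, because reference ranges are requested only on the NIS AE form (Protocol 13.2). When baseline is at least half the ULN, a rise above 2-fold implies a value above the ULN (1.2/2 = 0.6 mg/dL in the example); otherwise the ULN must be confirmed.

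**The case against.** The strongest reply is that this study is designed to count reported events. Protocol 8.3.2.1 bases the safety endpoints on reported adverse events, and several duties make a miss less likely. Protocol 10.1 gives an abnormal laboratory finding as an example of an AE. Visits 2 and 3 ask for clinically significant laboratory changes. AESIs must be closely monitored and reported within 24 hours, and eCRF data are verified against source. This stands as a reason to expect few misses. But these duties all rely on recognition at the site, and none is a stated comparison of the stored values with the AE records.

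Two practical objections also stand. Baseline creatinine is the latest available result with no time window, whereas effectiveness laboratory data must be within one month of baseline, so an old baseline could create false flags. And confirming the ULN needs queries to sites.

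Some stronger readings are tempting but not supported:

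- That the AESI is counted only through investigator entry. No sentence says so; it is inferred from the AE-based route and the absence of a derivation. The data management plan, the eCRF and the text of SAP 6.8.3 (cited in 6.8) were not available, and any of them could hold a check.
- That rises below the threshold would be counted. Footnote d puts the threshold inside the SAP's AESI definition, so a smaller rise does not qualify by the plan's own terms.
- That creatinine is analysed only as a mean change. SAP 5.3 adds the median, minimum and maximum.
- That the database already holds complete proof of each event. It can hold the doubling, but no ULN is among the listed visit items.

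**Conclusion.** The point holds as a cheap improvement. A numerical AESI definition and the values needed to test most of it are both in the plan, but no stated step brings them together. The described summaries do not identify a doubling per patient and leave out a Visit 2 rise that resolved. A recorded doubling without an AE entry could therefore be absent from a listed safety endpoint.

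The size is unknown. The rates and entry shares above are assumptions that show only how sensitive small counts are, and the exact intervals for 1 and 3 cases in 600 overlap widely. A reader might infer that cases will be missed, or that the reported incidence will be too low by some factor. The documents support neither: they show that a safeguard is not stated, not that events go unreported. The conclusion would fall away if the data management plan or the eCRF specification already contains this reconciliation.

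**What to change.** 1. In SAP 7.1, derive a flag for any recorded Visit 2 or Visit 3 creatinine more than 2 times the recorded baseline value. Use both visits, not only the final one.
2. Before database lock, query each flagged patient who has no matching AE. Confirm the laboratory's ULN and the date of the baseline value.
3. In SAP 6.8.1 or 6.8.5, report the confirmed laboratory-derived count beside the investigator-reported AESI count. Use patients with both a baseline and a follow-up creatinine as the denominator, and state that number. The choice matters: 3 cases are 0.50% of 600 but 1.00% of 300.
4. If such a check already exists in the data management plan or eCRF, cite it in the SAP and add only the side-by-side count.

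**Cost.** A short derivation, a small number of ULN queries, and some false flags where the baseline value is old. No new tests are needed. SAP 7.1 already allows extra derived variables to be specified in the tables without revising the SAP. Coverage stays limited to patients whose tests were available. The same derivation cannot be offered for the hepatic AESI, because AST, ALT and bilirubin are not listed as routine visit items.
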